4.2.2.2 Restrictions on diet and life style

Because psychoactive drugs may impair thinking, judgment, and/or motor skills, subjects will be cautioned about operating machinery, including automobiles, until they are reasonably certain that the study medication does not adversely affect their ability to engage in such activities.

Subjects should not abuse of alcohol or drugs during study as defined in the 5th edition of the Diagnostic and Statistical Manual of Mental Disorders (DSM-V), or in the opinion of the investigator, or as indicated by a positive urine drug screen for cocaine, opioid, PCP, amphetamine, heroin, or marijuana during the trial.

There are no other restrictions on diet, exercise, or smoking except that the patient's usual habits, including nicotine and caffeine intake, should not be drastically changed. Also refer to Section 4.1.4 for further intake guidelines.

4.3 TREATMENT COMPLIANCE

Subjects who are non-compliant, e.g., they do not appear for treatment or violate the restrictions, may be withdrawn from the trial at the discretion of the investigator and the eCRF will be completed accordingly (for further procedures cf. Section 6.2.3). If a patient withdraws during the treatment period, after first administration of the study drug, a complete post examination, done at EOT, will be performed.

Compliance will be assured by administration of all study medication under supervision of the investigating physician or a designee.

BI Trial No.: 1289.27

Doc. No.: c02218444-07 Trial Protocol Revision 3 Page 41 of 101

5. VARIABLES AND THEIR ASSESSMENT

5.1 EFFICACY - CLINICAL PHARMACODYNAMICS

5.1.1 Endpoints of efficacy

Efficacy measurements will not be performed.

5.1.2 Assessment of efficacy

Not applicable

5.2 SAFETY

5.2.1 Endpoints of safety

Primary endpoint:

• The number (%) of subjects with AEs, coded to the MedDRA-SOC 'Eye disorders', as determined by the investigator at End of Trial

Secondary endpoint:

• The number (%) of subjects with drug-related AEs as determined by the investigator at End of Trial

Further safety and tolerability will be assessed in a descriptive way based on:

- Adverse events (ocular and systemic)
- •

• Occurrence of Protocol-specified AESI (adverse events of special interest)

5.2.2 Assessment of adverse events

Safety assessments will consist of monitoring and recording all adverse events (AEs) and serious adverse events (SAEs) and includes clinically significant ophthalmological findings, EEGs, periodic physical examinations, measurement of vital signs, assessment of cardiac function with periodic ECGs and 24-hour heart rate monitoring, monitoring of laboratory tests (i.e. haematology, chemistry, coagulation, urine analysis), pregnancy test etc., as outlined in the Flow Chart. Ocular and systemic safety will be captured and analysed separately.

5.2.2.1 Definitions of adverse events

Adverse event

An adverse event (AE) is defined as any untoward medical occurrence in a patient or clinical investigation subject administered a pharmaceutical product and which does not necessarily have to have a causal relationship with this treatment.

An AE can therefore be any unfavourable and unintended sign (including an abnormal laboratory finding), symptom, or disease temporally associated with the use of a medicinal product, whether or not considered related to the medicinal product.

Serious adverse event

A serious adverse event (SAE) is defined as any AE which:

- results in death,
- is life-threatening,
- requires inpatient hospitalisation or prolongation of existing hospitalisation,
- results in persistent or significant disability or incapacity,
- is a congenital anomaly/birth defect,
- is to be deemed serious for any other reason if it is an important medical event when based upon appropriate medical judgment which may jeopardize the patient and may require medical or surgical intervention to prevent one of the other outcomes listed in the above definitions.

Life-threatening in this context refers to an event in which the patient was at risk of death at the time of the event; it does not refer to an event that hypothetically might have caused death if more severe.

Every occurrence of cancer or exacerbation of an existing cancer must be reported as a serious event regardless of the duration between discontinuation of the drug and the occurrence of the cancer.

AEs considered "Always Serious"

In accordance with the European Medicines Agency initiative on Important Medical Events, Boehringer Ingelheim has set up a list of AEs, which by their nature, can always be

Proprietary confidential information.

Doc. No.: c02218444-07

Page 43 of 101

considered to be "serious" even though they may not have met the criteria of an SAE as given above.

The latest list of "Always Serious AEs" can be found in the RDC system.

Adverse events of special interest (AESIs)

The term AESI relates to any specific AE that has been identified at the project level as being of particular concern for prospective safety monitoring and safety assessment within this trial, e.g. the potential for AEs based on knowledge from other compounds in the same class. AESI need to be reported to the Sponsor's Pharmacovigilance Department within the same timeframe that applies to SAE, see Section 5.2.2.2.

The following are considered as AESIs:

- Hepatic injury
 - A hepatic injury is defined by the following alterations of hepatic laboratory parameters:
 - An elevation of AST and/or ALT ≥3 fold ULN combined with an elevation of total bilirubin ≥2 fold ULN measured in the same blood draw sample, and/or
 - Marked peak aminotransferase (ALT, and/or AST) elevations ≥10 fold ULN

These lab findings constitute a hepatic injury alert and the subjects showing these lab abnormalities need to be followed up according to the drug-induced liver injury (DILI) checklist provided in the ISF. In case of clinical symptoms of hepatic injury (icterus, unexplained encephalopathy, unexplained coagulopathy, right upper quadrant abdominal pain, etc.) without lab results (ALT, AST, total bilirubin) available, the investigator should make sure these parameters are analysed, if necessary in an unscheduled blood test. Should the results meet the criteria of hepatic injury alert, the procedures described in the DILI checklist should be followed.

- Clinically significant loss of vision (assessed by BCVA) based on investigator's judgment
- Clinically significant change of color vision (assessed by F-M 100) based on investigator's judgment
- Marcus Gunn pupil sign
- Acute corneal edema
- Increase of IOP \geq 30 mmHg
- Retinal vascular occlusion and/or retinal hemorrhage or edema
- Blurred papillary margin (papillary-edema)

Intensity of AEs

The intensity of the AE should be judged based on the following:

Mild: Awareness of sign(s) or symptom(s) that is/are easily tolerated Moderate: Enough discomfort to cause interference with usual activity

Severe: Incapacitating or causing inability to work or to perform usual activities

BI Trial No.: 1289.27 Doc. No.: c02218444-07 **Trial Protocol Revision 3** Page 44 of 101

Causal relationship of AEs

Medical judgment should be used to determine the relationship, considering all relevant factors, including pattern of reaction, temporal relationship, de-challenge or re-challenge, confounding factors such as concomitant medication, concomitant diseases and relevant history.

[figure not shown]
Yes: There is a reasonable causal relationship between the investigational product administered and the AE.

There is no reasonable causal relationship between the investigational product No: administered and the AE.

5.2.2.2 Adverse event collection and reporting

AE Collection

The following must be collected and documented on the appropriate eCRF by the Investigator from signing the informed consent onwards through the Residual Effect period REP), until individual patient's End of Trial, all AEs (serious and non-serious), and AESIs.

The REP is defined as 7 days after the last trial medication application. All AEs which occurred through the treatment phase and throughout the REP will be considered as on treatment (cf. Section 7.3.3). Events which occurred after the REP will be considered as post treatment events.

After the individual patient's End of Trial the investigator does not need to actively monitor the patient for AEs but should only report relevant SAEs and relevant AESIs of which the investigator may become aware of through the SAE reporting process, not on eCRF.

AE reporting to sponsor and timelines

The Investigator must report SAEs, AESIs, and non-serious AEs which are relevant for the reported SAE or AESI, on the BI SAE form via fax immediately (within 24 hours) to the Sponsor's (SAE form and specific contact details will be provided in the ISF). The same timeline applies if follow-up information becomes available. In specific occasions the Investigator could inform the Sponsor upfront via telephone. This does not replace the requirement to complete and fax the BI SAE form.

Doc. No.: c02218444-07 Trial Protocol Revision 3 Page 45 of 101

Information required

For each AE, the Investigator should provide the information requested on the appropriate (e)CRF pages and the BI SAE form, e.g. onset, end date, intensity, treatment required, outcome, seriousness, and action taken with the investigational drug(s). The Investigator should determine the causal relationship to the trial medication and any possible interactions between the investigational drug(s) and a Non-Investigational Medicinal Product (NIMP).

The following should also be recorded as an (S)AE in the (e)CRF and SAE form (if applicable):

- Worsening of the underlying disease or of other pre-existing conditions
- Changes in vital signs, ECG, physical examination and laboratory test results, if they are judged clinically relevant by the Investigator.

If such abnormalities already pre-exist prior trial inclusion they will be considered as baseline conditions.

All (S)AEs, including those persisting after trial completion must be followed up until they have resolved, have been sufficiently characterized, or no further information can be obtained.

Pregnancy

In the rare case that a female subject participating in this clinical trial becomes pregnant after having taken trial medication, the Investigator must report immediately (within 24 hours) the drug exposure during pregnancy (DEDP) to the Sponsor's (form and specific contact details will be provided in the ISF). The Pregnancy Monitoring Form for Clinical Trials (Part A) should be used.

The outcome of the pregnancy associated with the drug exposure during pregnancy must be followed up and reported to the Sponsor's unique entry point on the Pregnancy Monitoring Form for Clinical Trials (Part B).

As pregnancy itself is not to be reported as an AE, in the absence of an accompanying SAE, only the Pregnancy Monitoring Form for Clinical Trials and not the SAE form is to be completed. If there is an SAE associated with the pregnancy then the SAE has to be reported on the SAE form in addition.

The ISF will contain the Pregnancy Monitoring Form for Clinical Trials (Part A and B).

5.2.3 Assessment of safety laboratory parameters

The laboratory tests listed in Table 5.2.3: 1 will be performed at the central laboratory service provider. Fasting is not required. Instructions on collection, handling/ processing, and shipping of the samples will be provided in the investigator site file by the central laboratory. For time points of laboratory sampling refer to the Flow Chart.

Laboratory results of the subjects will be available to the respective investigator and to the BI Clinical Monitor (central laboratory website), and selected abnormal laboratory alerts will be sent automatically to the sites and to the sponsor within 24 hours.

Doc. No.: c02218444-07

Page 46 of 101

Clinically relevant laboratory values should be commented on lab report print-outs if there is no validated and certified e-medical record for the comments of laboratory data. A clinically relevant value may be either in- or outside the reference range. Clinically relevant abnormal laboratory test results must be confirmed using an unscheduled visit lab kit and should be repeated until normalisation or stabilisation or until an alternative explanation has been found.

Table 5.2.3: 1 Routine Laboratory test

Haematology Hematocrit (Hct) Hemoglobin (Hb) Red Blood Cell Count/ Erythrocytes (RBC) Reticulocyte Count White Blood Cells / Leukocytes (WBC) Platelet Count/ Thrombocytes	 Differential. Automatic (manual if differential automatic is abnormal) Neutrophils Eosinophils Basophils Monocytes Lymphocytes
Coagulation • Partial Thromboplastin Time (=aPTT)	• Prothrombin time (Quick and INR)
 Chemistry AST(SGOT) ALT(SGPT) Alkaline Phosphatase (AP) Albumin Creatine Kinase (CK) CK-MB, only if CK is elevated Gamma-Glutamyl Transferase (GGT/γ-GT) Lactic Dehydrogenase (LDH) Calcium Sodium Potassium Chloride Bicarbonate 	 Glucose Creatinine BUN Bilirubin Total Bilirubin Direct Bilirubin Indirect Protein Total Uric Acid Cholesterol Total Triglycerides
Pregnancy test (females only)	Human urine chorionic gonadotropin
Urinalysis¹ (Stix) • Urine Nitrite • Urine Protein • Urine Glucose • Urine Ketone • Urobilinogen	 Urine Bilirubin Urine RBC/ Erythrocytes Urine WBC/ Leukocytes Urine pH Urine creatinine
Urine-Sediment (microscopic examination), (only if urine analysis abnormal) Urine Sediment Bacteria Urine Cast in Sediment	 Urine Squamous Epith Cells Urine Sediment RBC/ Erythrocytes Urine Sediment WBC/ Leucocytes

At screening, baseline andend of trial.

Proprietary confidential information.

Doc. No.: c02218444-07

Page 47 of 101

The following tests will be performed only at screening examination; the results will not be part of the Clinical Trial Report. Exclusionary testing may be repeated during the screening period if necessary. Subjects must have a negative drug screening prior to inclusion in the study.

Table 5.2.3: 2 Exclusionary Laboratory test (screening visit only)

Drug Screening (Urine)

- Cannabis
- Barbiturates
- Opiates

- Cocaine
- Amphetamines
- Methadone
- Phencyclidine

5.2.4 Electrocardiogram

The 12-lead ECGs will be performed as scheduled in the Flow Chart. ECG will be recorded after the subjects have rested for at least 5 minutes in a supine position. The investigator or a designate will evaluate whether the ECG is normal or abnormal and whether it is clinically significant, if abnormal. The electronic version of the ECG is regarded as source data. Dated and signed printouts will be stored in the patient's medical file if there is no validated and certified e-medical record for ECG data.

ECGs may be repeated for quality reasons and the repeat used for analysis. Additional ECGs may be collected by the investigator for safety reasons. The recordings will be checked for pathological results (to be reported as baseline conditions or AEs) by the investigator. Any ECG abnormalities will be carefully monitored and if necessary the patient will be removed from the trial and medically treated. Baseline will be the measurements taken prior to the first administration. Notable findings are defined as occurrence of any QTc interval from any individual >450 ms, >480 ms or >500 ms or the occurrence of any individual increase from baseline by >30 ms or >60 ms.

5.2.5 Physical examination

The physical examination will be carried out within -28 to -3 days before the study (Screening), on Day -2 or -1 (Baseline), Day 7 and End of Trial examination (7-14 days after the last drug administration for each patient). At the screening visit, a complete medical examination will include documentation of patient information, informed consent, demographics including height and weight, smoking and alcohol history, relevant medical history and concomitant medication, review of inclusion/exclusion criteria, review of vital signs (BP, PR), 12-lead ECG and laboratory, and a physical examination. At the End of Trial examination, it will include review of vital signs, 12-lead ECG and laboratory, and a physical examination. Adverse events and concomitant therapies will be assessed throughout the study.

Physical examination will include weight and an examination of general appearance, skin, lungs, heart, abdomen, lymph nodes, extremities and basic nervous system evaluation.

Page 48 of 101

Information about the physical examination must be present in the source documentation at the study site. Physical examination and ECG data are not collected on eCRF, however, any significant findings made after the start of study drug which meet the definition of an AE must be recorded as the Adverse Event in eCRF.

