7. STATISTICAL METHODS AND DETERMINATION OF SAMPLE SIZE

7.1 STATISTICAL DESIGN - MODEL

This is a Phase Ic, randomised, parallel-group, double-blind study.

The primary objective is to investigate the ocular safety of BI 409306 in patients with schizophrenia, Alzheimer's disease, and age-comparable healthy volunteers following oral administration of 25 mg and 100 mg over 14 days.

The primary endpoint is number (%) of subjects with AEs, coded to the MedDRA-SOC 'Eye disorders', as determined by the investigator at End of Trial.

The secondary objectives are the evaluation of systemic safety and exploration of the pharmacokinetics of BI 409306.

Secondary endpoints include the number (%) of subjects with drug-related AEs as determined by the investigator at End of Trial. Secondary endpoints also include the following pharmacokinetic parameters of BI 409306:

- $C_{max,ss}$ maximum measured concentration of the analyte in plasma at steady-state (Day 14).
- t_{max,ss} time from dosing to maximum measured concentration of the analyte in plasma at steady-state (Day 14).

The derivation of the PK parameters is given in Appendix Section 10.1.

No statistical testing will be performed on the primary and secondary endpoints.

General tolerability will be evaluated on the basis of the following investigations: physical examination, vital signs (BP, PR), 12-lead ECG (electrocardiogram), clinical laboratory tests (haematology, clinical chemistry and urinalysis) and adverse events.

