7.8.4 ECG

Clinically significant findings for ECG will be recorded as baseline conditions or AEs and will be analyzed accordingly.

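### The protocol defines QTc categories for notable findings, but neither the planned data capture nor the SAP allows them to be counted

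*Protocol*

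**What the plan says.** Protocol 5.2.4 gives numeric rules. For absolute values: "Notable findings are defined as occurrence of any QTc interval from any individual >450 ms, >480 ms or >500 ms". For change: "occurrence of any individual increase from baseline by >30 ms or >60 ms". The same section fixes the reference point ("Baseline will be the measurements taken prior to the first administration"), allows for repeats ("ECGs may be repeated for quality reasons and the repeat used for analysis") and says where the recording is kept ("The electronic version of the ECG is regarded as source data"). It also has the investigator or a designate read every ECG as normal or abnormal and judge clinical significance, with pathological results reported as baseline conditions or AEs.

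Protocol 5.2.5 says: "Physical examination and ECG data are not collected on eCRF". Under that section, a significant finding after the start of study drug reaches the eCRF only as an AE.

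Protocol 7.1 names the ECG as a basis for tolerability: "General tolerability will be evaluated on the basis of the following investigations: physical examination, vital signs (BP, PR), 12-lead ECG". Protocol 5.4 adds that the scheduled measurements are suitable for detecting drug-induced ECG changes.

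SAP 7.8.4 reads: "Clinically significant findings for ECG will be recorded as baseline conditions or AEs and will be analyzed accordingly". SAP section 4 declares no change from the protocol's planned analysis.

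**The concern.** A threshold on QTc, and even more a threshold on change from baseline, needs numeric values for each subject and visit. The protocol sets both kinds of threshold, defines the baseline and mentions a repeat being used for analysis, all of which reads as an analysis rule. The capture and analysis sections provide neither the values nor an output.

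The consequence is a safety report that depends on a judgement the thresholds were meant to supplement. An interval can meet the 5.2.4 definition and still leave no trace in the results. If the investigator does report it, it appears as an AE term with no value, no category and no denominator. A reader who knows the 5.2.4 definition could take a report without QTc findings to mean that no threshold was crossed, which the planned data cannot show. This matters because protocol 1.2.2 and 2.3 describe the toxicological profile as characterised by cardiac effects, and 1.2.2 asks for careful monitoring of cardiac function.

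**Working it through.** The plan states no figure to reproduce. The check follows a 12-lead QTc value through the documents and then counts recordings.

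**Data path**

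| Step | Where | What it provides |
|---|---|---|
| Definition | Protocol 5.2.4 | Three absolute and two change criteria, a baseline, a rule on repeats |
| Recording | Protocol 5.2.4 | Electronic ECG kept as source |
| eCRF | Protocol 5.2.5 | ECG data excluded; only findings meeting the AE definition are entered |
| Source-to-eCRF list | Protocol 8.3.1 | No ECG item |
| External transfer | Protocol 5.2.7 and 8.2 | Central ECG vendor and centralised monitoring described for Holter only |
| Protocol analysis | Protocol 7.3.3 | Other safety-relevant data compared with pre-treatment findings; no ECG or QTc output named |
| SAP analysis | SAP 7.8.4 | Clinically significant findings, as baseline conditions or AEs |
| SAP abbreviations | SAP section 2 | QRS and RR listed; QT and QTc not listed |

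The path breaks between recording and database, and again at analysis. The readable text also names no QT correction formula, so QTc is not fully defined even where it is measured.

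**Two examples.** A post-dose QTc of 460 ms exceeds 450 ms. A rise of 35 ms exceeds 30 ms. Each is a notable finding under 5.2.4. If judged not clinically significant, neither is an AE under 5.2.5, so neither enters SAP 7.8.4.

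**Scale.** The flow chart schedules 12-lead ECGs at Screening, Day 1, Day 7, Day 14 and EOT, which is 5 per subject. Protocol 7.6 plans 60 subjects.

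- All scheduled ECGs: 5 x 60 = 300.
- Flow chart footnote 4 puts ECGs before dosing, so the Screening and Day 1 recordings precede any drug: 2 x 60 = 120.
- After the first dose (Day 7, Day 14, EOT): 3 x 60 = 180. Only these can meet a change criterion.

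**What the post-first-dose ECGs show.** Protocol 1.2.4 gives a plasma terminal half-life of 1.28 to 2.35 h in trial 1289.3. Once-daily dosing puts the Day 7 and Day 14 pre-dose ECGs roughly 24 h after the previous dose: 24 / 2.35 = 10.2 half-lives at the slow end and 24 / 1.28 = 18.8 at the fast end. The EOT ECG comes 7 to 14 days after the last dose. Poor metabolisers have 4.1 to 5.0 times the total exposure of extensive metabolisers (1.2.4), so they may retain more drug at trough. For most subjects the intervals would still be trough or post-washout values.

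**The case against.** The strongest reply is that the reporting chain is coherent and no section promises a QTc table. Every ECG is read, pathological results become baseline conditions or AEs, and the SAP analyses those. The amendment log shows that keeping ECG data off the eCRF was deliberate. On that view the thresholds only prompt the investigator, and 7.1 is satisfied through AE reporting, as it is for physical examination, which is also kept off the eCRF. This is a tenable design, but 5.2.4 does not say that this is what it means. Its baseline, change thresholds and reference to analysis point the other way, so the passages still need reconciling.

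Several stronger readings are tempting, and the documents do not support them:

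- **That the thresholds could never be tabulated, or that no QTc values exist.** Electronic ECGs are kept as source and could be retrieved. The gap is in planned capture and analysis.
- **That a report without ECG findings would reflect missing data.** Each recording is assessed, so the absence would mean that no finding was judged reportable. That is a less sensitive standard than the thresholds, but the ECGs were examined.
- **That a QT-prolongation signal is being overlooked.** The documented signal is mainly heart rate. Dogs showed shortened RR, PR and QT intervals at the highest telemetry dose (1.2.1), and earlier human trials showed no relevant ECG changes beyond a short-lived pulse increase in poor metabolisers (1.2.3). That signal is followed by serial Day 1 pulse rates and 24-hour Holter monitoring.
- **That 12-lead ECG should be struck from 7.1.** ECGs are performed, read and reported through baseline conditions and AEs, so removing them would make 7.1 less accurate.

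The pre-dose timing also stands as an objection to overselling the remedy: the table would apply the stated rule but would not assess QTc at peak concentration.

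**Conclusion.** The inconsistency is real and limited. The protocol's five QTc criteria cannot be applied to the data and analyses as planned, and ECG safety rests on investigator judgement alone. It concerns 300 scheduled ECGs, 180 of them after the first dose, and those 180 mainly reflect trough or washed-out drug levels. The primary endpoint is unaffected.

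This assumes full enrolment of 60 with all scheduled ECGs done, and that the blacked-out parts of the documents contain no 12-lead data transfer or QTc output. Some SAP sections and protocol safety bullets are not readable, but SAP 7.8.4 reads as complete.

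**What to change.** Reconcile protocol 5.2.4, 5.2.5 and 7.1 with SAP 7.8.4 in one of two ways.

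**Preferred: apply the rule.**
- Transfer HR, QT and QTc for each scheduled ECG from the existing electronic recordings, or add three eCRF fields.
- Name the QT correction formula.
- Add one table to SAP 7.8.4 giving the number and percentage of subjects in each 5.2.4 category by dose and population, with denominators. Limit the two change categories to ECGs after the first dose.
- Add a note that ECGs were taken pre-dose, so the values mainly describe trough or post-washout intervals.

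The cost is transfer or entry of three values on up to 300 recordings, plus one table. No new ECG or procedure is needed. With 60 / 6 = 10 subjects per dose-by-population cell, one subject is 10%, so the table is descriptive only.

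**Otherwise: limit the claim.** State in 5.2.4 that the thresholds are only a flag for investigator review and that no QTc analysis is planned. Keep 12-lead ECG in 7.1, noting that it is evaluated through baseline conditions and AEs. This costs a text edit, and the trial then reports no QTc category counts.
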